6.1.1.3 Dose Selection and Timing

The CYD dengue vaccine will be administered in 3 doses with a 6-month interval between each dose as per the indication obtained for the vaccine licensed in Brazil.

6.1.2 Identity of Control Product

6.1.2.1 Composition

Product: Placebo
Form: Solution
Vaccine: NaCl 0.9%
Route: SC
Batch number: To be determined

6.1.2.2 Preparation and Administration

The product must be stored between +2°C and +8°C.

The placebo must be removed from refrigerator. The placebo should not be used if particles are present in the solution. The placebo will be administered subcutaneously in the deltoid region of the upper arm in a volume of 0.5 mL.

6.1.2.3 Dose Selection and Timing

Not applicable.

6.2 Identity of Other Product

Not applicable.

6.3 Product Logistics

6.3.1 Labeling and Packaging

CYD dengue vaccine and placebo will be supplied in vials/syringes and will be labeled and packaged according to national regulations. The information on the label will include:

- Study code
- Name of product and Group assignment
- Route of injection
- Investigational use only statement
- Storage conditions
- Batch number
- Name of Sponsor

- Expiry date

All the products will be identified for Group assignment by a dose number

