- If a subject is eligible but not randomized during the ESDR hold, the subject will be asked to come back to the site after the hold. The subject will then be re-screened and randomized. However, the subject will not be re-tested for previous exposure to dengue by RDT or IgG ELISA. It is to be noted that subjects that are re-screened will be allocated a new subject number.

Visit 1 (Inj 1 /D0): Randomization, Blood Sample, and Vaccination of Eligible Subjects

Once dengue previous exposure has been identified using RDT or dengue IgG ELISA, the Visit 1 procedures may be undertaken.

- 1) Review the inclusion and exclusion criteria and confirm the eligibility
- 2) Collect demographic (year of birth and gender) and body stature (height and weight) data
- 3) Check and collect the subject's significant medical history (including ART-related information)
- 4) Check and collect the subject's history of dengue vaccination/infection, of YF vaccination/infection, and of Zika infection
- 5) Perform a physical examination and record the subject's axillary temperature before injection
- 6) Check concomitant medications and record every reportable medication ongoing at the time of vaccination
- 7) Perform a urine pregnancy test for all women enrolled in the study
- 8) Obtain a blood sample (see [Section 7.1](#) for detailed instructions regarding the handling of blood samples), record the date of collection

It is important to note that, if the attempt(s) to collect blood is (are) unsuccessful, the subject should be given the opportunity for another attempt. If a blood sample cannot be obtained, the reason will be recorded in the blood sampling page of the CRF.

- 9) The person in charge of injections (“vaccinator”) or authorized designee contacts the IRT to obtain the assigned product to be administered
- 10) Inject the appropriate investigational product
- 11) Record the date of injection, the site, and side of injection and the route of administration, as well as the dose number of the vaccine
- 12) Affix the vaccine labels in the subject’s source documents
- 13) Keep the subject under observation for 30 minutes, and record any immediate AE reaction in the source document
- 14) Give the subject the first DC (DC1) to record any injection site reactions and systemic AEs, together with instructions for its completion, including explanations on the definition and use of intensity scales for collection of AEs

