Note: A follow-up visit can be arranged depending on the information provided during the phone call, at the Investigator's discretion.

Visit 6 (Inj 2+28D [+14 days]): Collection of Safety Information and Blood Sample

- 1) Collect DC3 and check the information entered into it by interviewing the subject and request information concerning any medical event, serious, or not, that may have occurred since Visit 5
- 2) Record any AEs and any reportable concomitant medications
- 3) Perform a physical examination and record the subject's axillary temperature (if necessary)
- 4) Remind the subject to call the study center if a serious medical event occurs
- 5) Obtain a blood sample (see [Section 7.1](#) for detailed instructions regarding the handling of blood samples), record the date of collection

It is important to note that, if the attempt(s) to collect blood is (are) unsuccessful, the subject should be given the opportunity for another attempt within the Visit window. If a blood sample cannot be obtained, the reason will be recorded in the blood sampling page of the CRF.

- 6) Provide the subject with DC4 and remind her/him to bring it back when she/he returns for Visit 7
- 7) Arrange an appointment for the next visit (V07; at V01 + 12 months (M12) [\pm 20 days])
- 8) Complete the relevant CRF pages for this visit

Visit 7 (Inj 3 [M12; \pm 20 days]): Collection of safety information and vaccination

Same procedure as for Visit 5. Subject is provided with DC5.

Phone Call 3 (Inj 3+7D [+3 days]): Safety Follow-up Phone Call

Same procedures as for Phone Call 1.

Phone Call 4 (Inj 3+14D [+3 days]): Safety Follow-up Phone Call

Same procedures as for Phone Call 2.

Visit 8 (Inj 3+28D [+14 days]): Collection of Safety Information and Blood Sample

- 1) Collect DC5 and check the information entered into it by interviewing the subject and request information concerning any medical event, serious, or not, that may have occurred since Visit 7
- 2) Record any AEs and any reportable concomitant medications
- 3) Perform a physical examination and record the subject's axillary temperature (if necessary)
- 4) Obtain a blood sample (see [Section 7.1](#) for detailed instructions regarding the handling of blood samples), record the date of collection

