6.1.1.2 Preparation and Administration

Sanofi Pasteur's CYD dengue vaccine consists of a powder and solvent for suspension for injection and must be stored between +2°C and +8°C (ie, in a refrigerator) and protected from light.

The vaccine must be removed from the refrigerator, reconstituted with the solvent supplied for this purpose, and used immediately after reconstitution.

The vaccine is to be administered subcutaneously in the deltoid region of the upper arm in a volume of 0.5 mL.

Prior to administration, all study products must be inspected visually for cracks, broken seals, correct label content (see [Section 6.3.1](#)), and extraneous particulate matter and / or discoloration, whenever solution, and container permit. If any of these conditions exists, the vaccine must not be administered. A replacement dose is to be used, and the event is to be reported to the Sponsor.

Subjects must be kept under observation for 30 minutes after each vaccination to ensure their safety, and any reactions during this period will be documented in the CRB. Appropriate medical equipment and emergency medications, including epinephrine (1:1000), must be available on site in the event of an anaphylactic, vasovagal, or other immediate allergic reaction.

If a vial or syringe is accidentally broken and the product spilled out, appropriate disinfection procedures must be used (please refer to the Operating Guidelines and/or study center's procedures).

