6.3.2.3 Product Accountability

The person in charge of product management at the site will maintain records of product delivery to the study site, product inventory at the site, the dose(s) given to each subject, and the disposal of, or return to the Sponsor of unused doses.

The necessary information on the product labels is to be entered into the source document and the CRB. If applicable, information may also be entered into the subject's vaccination card.

The Sponsor's monitoring staff will verify the study site's product accountability records against the record of administered doses in the CRBs and the communication from the IRT (if applicable).

In case of any expected or potential shortage of product during the study, the Investigator, or an authorized designee should alert the Sanofi Pasteur representative as soon as possible, so that a shipment of extra doses can be arranged.

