6.4 Blinding and Code-breaking Procedures

An observer-blind procedure will be followed for the injection of CYD dengue vaccine or placebo. Neither the observer Investigator, nor the Sponsor, nor the subjects know which product will be administered. The “vaccinator” will be in charge of preparing and administering the products and will not be authorized to collect any safety data, nor will she/he be involved in safety assessment. In addition, the “vaccinator” or authorized designee will have to ensure that the documents on randomization are stored in a secure place where only she/he has access.

The code may be broken in the event of an AE only when the identification of the vaccine received could influence the treatment of the subject. Code-breaking should be limited to the subject(s) experiencing the AE.

The blind can be broken by the Investigator or a delegate through the IRT system, as explained in the code-breaking procedures described in the Operating Guidelines. Once the emergency has been addressed by the site, the Investigator, or a delegate must notify the Sanofi Pasteur RMO if a subject’s code was broken. All contact attempts with the Sponsor prior to unblinding are to be documented in the source documents, and the code-breaking CRF is to be completed.

A request for the code to be broken may also be made:

- by the GPV Department through an internal system for reporting to health authorities in the case of an SAE as described in International Conference on Harmonisation (ICH) E2A. In this case, the code will be broken only for the subject(s) in question. The information resulting from code-breaking (ie, the subject’s vaccine or Group assignment) will not be communicated to either the Investigator or the immediate team working on the study, except for the GPV representative.
- by the IDMC if needed to facilitate their assessment of safety.

The IEC / IRB must be notified of the code-breaking. All documentation pertaining to the event must be retained in the site’s study records and in the Sanofi Pasteur files. Any intentional or unintentional code-breaking must be reported, documented, and explained, and the name of the person who requested it must be provided to the Sponsor.

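### Does filing product labels in the source documents undo the observer blind?

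*Protocol*

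**What the plan says.** **Label content.** Protocol 6.3.1 lists "Name of product and Group assignment" and the batch number among the label items. The same section closes with "All the products will be identified for Group assignment by a dose number". Section 6.1.1.2 requires products to be "inspected visually for cracks, broken seals, correct label content" before use and refers back to 6.3.1.

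**Where labels go.** In 5.1.4, Visit 1 step 12 and Visit 5 step 10 both begin "Affix the vaccine labels in the" and name the subject's source documents as the destination. Visit 7 reads "Same procedure as for Visit 5". No role is named for this step.

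**Transcription and checking.** Section 6.3.2.3 states: "The necessary information on the product labels is to be entered into the source document and the CRB". Sponsor monitoring staff then verify "product accountability records against the record of administered doses in the CRBs and the communication from the IRT".

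**The blind.** Section 6.4 states: "Neither the observer Investigator, nor the Sponsor, nor the subjects know which product will be administered". It has a separate vaccinator prepare and give the products, bars that person from collecting or assessing safety data, and restricts access to the randomization documents. Section 6.5 adds that dose numbers come from a random list that does not reveal the group, and that the dose number is what is entered in the case report book.

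**The concern.** If the label prints the actual product name and is stuck in the subject's file, anyone who opens that file could learn the allocation. The investigator assessing adverse events works from source documents, and 13.4.1 gives Sponsor staff direct access to subject files. Both are blinded parties under 6.4. Random dose numbers do not hide a printed name, and the access restriction in 6.4 mentions only randomization documents. Section 6.3.2.2 also makes the Investigator or a designee responsible for product without requiring that person to be outside safety assessment. The stock itself is telling, because the vaccine is reconstituted (6.1.1.2) and the placebo is a solution (6.1.2.2).

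At stake are the judgements that the blind protects:

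- investigator causality for unsolicited systemic events, which feeds the early safety review (5.1.6) and the descriptive tables (12.1.1.2);
- investigator or Sponsor causality for the hold after three related serious events (5.5);
- the decision that a CD4 fall or HIV-1 RNA rise has no other explanation (5.5, 10.7).

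**Working it through.** The documents give no figure to reproduce, and a bias size would need facts they do not contain. The check sets the sections side by side and then counts where a leaked allocation could enter the results.

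**1. Each possible route to unblinding**

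| Route | Text that raises it | Text that answers it | What stays open |
|---|---|---|---|
| Group printed on label | 6.3.1 list | 6.3.1 closing line: group is identified by dose number; 6.5: numbers are random | Nothing of substance |
| Product name or batch on label | 6.3.1 list | 6.4 rule that observer and Sponsor do not know the product | Whether the name is masked or the filed part omits it |
| Label check before use | 6.1.1.2 | 6.4: preparation is the vaccinator's task | Nothing of substance |
| Label filed in source documents | 5.1.4, 3 visits | Follows the IRT contact and injection steps, the first of which names the vaccinator or designee; 13.2 defines source documents broadly, so label and event notes need not share a page | No role is named for filing |
| Label data in case report book | 6.3.2.3 | Only what is necessary is entered; 6.5 and the visit steps name the dose number, not the product name or batch | Little |
| Stock differs in form | 6.1.1.2, 6.1.2.2 | The usual reason for a separate vaccinator, provided in 6.4; restricted storage in 6.3.2.2 | Whether the product manager may also assess safety |

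Two details remain open: the content of the filed label part, and the roles of those who file labels and manage stock. Section 6.4 already fixes the outcome that both must respect. Section 13.4.1 leaves detailed product management to the Operating Guidelines.

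**2. Which reading fits the whole text**

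Random dose numbers that conceal the group would do little if the same label printed the arm. A masked or generic product name, or a filed portion showing only the dose number, fits 6.3.1, 6.4 and 6.5 together. The text does not prove this reading. The literal one requires a site to disregard 6.4.

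**3. Where a leak would matter**

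- Primary endpoints in 9.1.1.2: 7, all worded as occurrence. Defined by relatedness: 0 of 7.
- Early safety review in 5.1.6: 4 groups of parameters, of which 1 (unsolicited events) is filtered by investigator relatedness.
- Hold signals in 5.5: 4, and all 4 carry some attribution condition. For the Grade 3 solicited reactions, relatedness is met by the convention in 9.1.1.3.5, although the search for another cause remains. The HIV-1 RNA and CD4 signals start from laboratory thresholds with a confirmatory test 4 weeks later. Only the signal of three related serious events rests mainly on causality.
- Hypotheses tested: none (12.1.1.1, 12.1.2.1).

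These counts show where judgement enters. They do not measure bias.

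**The case for a change.** The strongest opposing case is that a governing rule is not a mechanism. Section 6.4 says who must stay blinded, but no sentence says that the filed label lacks the product name or that the page is kept from the observer. Section 5.1.2 relies on the observer-blind design to limit bias in the safety assessments. There is also an indirect path to a primary endpoint: under 10.7, a CD4 or HIV-1 RNA change becomes a serious adverse event only if non-adherence and other causes are excluded. An unblinded assessor could therefore influence the count of serious events, even though that endpoint is not defined by relatedness. A one-line clarification would cost little.

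The textual observation stands, and so does the indirect path through 10.7. Neither shows that the plan as written produces unblinding. The path needs a blinded assessor who has in fact seen an arm-specific name, and nothing in the documents establishes that. The stricter remedies are not free either. Label content must follow national regulations (6.3.1), and if the accountability log names the product, the monitor checking it would have to sit outside the blinded team. Those are operating choices, and more than one arrangement would satisfy 6.4.

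**Conclusion.** The concern does not call for a change. It identifies an unstated operating detail that trained site staff would fill in line with 6.4. The blinding rule, the separate vaccinator, the random dose numbers and restricted storage are all in the protocol, and following them together preserves the blind. A cross-reference from 6.3.1 to the Operating Guidelines would make for tidier reading, but no result depends on it.

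The point is minor in size: one unspecified step repeated at 3 visits, 0 of 7 primary endpoints defined by relatedness, and no estimate, interval or sample-size statement altered.

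The conclusion rests on two assumptions: that the product name on the label is masked, or that the labelled page is kept from observers and monitors; and that whoever manages stock does not assess safety. The Operating Guidelines were not available to confirm either. If they had full labels filed alongside adverse event notes, or a safety assessor handling stock, the question would reopen as a matter of conduct.

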6.3.2 Product Shipment, Storage, and Accountability

6.3.2.1 Product Shipment

The Clinical Logistics Coordinator or designee will contact the Investigator or a designee to determine the dates and times of delivery of products.

Each vaccine shipment will include a temperature-monitoring device to verify maintenance of the cold-chain during transit. On delivery of the product to the site, the person in charge of product receipt will follow the instructions given in the Operating Guidelines, including checking that the cold-chain was maintained during shipment (ie, verification of the temperature recorders). If there is an indication that the cold-chain was broken, this person should immediately quarantine the product, alert the Sanofi Pasteur representative, and request authorization from Sanofi Pasteur to use the product.

6.3.2.2 Product Storage

The Investigator will be personally responsible for product management or will designate a staff member to assume this responsibility.

At the site, products must be kept in a secure place with restricted access. Vaccines will be stored in a refrigerator at a temperature ranging from +2°C to +8°C and should be protected from light. The vaccines must not be frozen. The temperature must be monitored and documented (see the Operating Guidelines) for the entire time that the vaccine is at the study site. In case of accidental freezing or disruption of the cold-chain, vaccines must not be administered and must be quarantined, and the Investigator, or authorized designee should contact the Sanofi Pasteur representative for further instructions.

6.3.2.3 Product Accountability

The person in charge of product management at the site will maintain records of product delivery to the study site, product inventory at the site, the dose(s) given to each subject, and the disposal of, or return to the Sponsor of unused doses.

The necessary information on the product labels is to be entered into the source document and the CRB. If applicable, information may also be entered into the subject's vaccination card.

The Sponsor's monitoring staff will verify the study site's product accountability records against the record of administered doses in the CRBs and the communication from the IRT (if applicable).

In case of any expected or potential shortage of product during the study, the Investigator, or an authorized designee should alert the Sanofi Pasteur representative as soon as possible, so that a shipment of extra doses can be arranged.

6.3.3 Replacement Doses

If a replacement dose is required (eg, because the syringe broke or particulate matter was observed in the syringe), the site personnel must either contact the IRT to receive the new dose allocation, or follow the instructions given in the Operating Guidelines.

6.3.4 Disposal of Unused Products

Unused or wasted products will be either disposed of or returned to the Sponsor in accordance with the instructions in the Operating Guidelines. Product accountability will be verified throughout the study period.

6.3.5 Recall of Products

If the Sponsor makes a decision to launch a retrieval procedure, the Investigators will be informed of what needs to be done.

6.4 Blinding and Code-breaking Procedures

An observer-blind procedure will be followed for the injection of CYD dengue vaccine or placebo. Neither the observer Investigator, nor the Sponsor, nor the subjects know which product will be administered. The “vaccinator” will be in charge of preparing and administering the products and will not be authorized to collect any safety data, nor will she/he be involved in safety assessment. In addition, the “vaccinator” or authorized designee will have to ensure that the documents on randomization are stored in a secure place where only she/he has access.

The code may be broken in the event of an AE only when the identification of the vaccine received could influence the treatment of the subject. Code-breaking should be limited to the subject(s) experiencing the AE.

The blind can be broken by the Investigator or a delegate through the IRT system, as explained in the code-breaking procedures described in the Operating Guidelines. Once the emergency has been addressed by the site, the Investigator, or a delegate must notify the Sanofi Pasteur RMO if a subject’s code was broken. All contact attempts with the Sponsor prior to unblinding are to be documented in the source documents, and the code-breaking CRF is to be completed.

A request for the code to be broken may also be made:

- by the GPV Department through an internal system for reporting to health authorities in the case of an SAE as described in International Conference on Harmonisation (ICH) E2A. In this case, the code will be broken only for the subject(s) in question. The information resulting from code-breaking (ie, the subject’s vaccine or Group assignment) will not be communicated to either the Investigator or the immediate team working on the study, except for the GPV representative.
- by the IDMC if needed to facilitate their assessment of safety.

The IEC / IRB must be notified of the code-breaking. All documentation pertaining to the event must be retained in the site’s study records and in the Sanofi Pasteur files. Any intentional or unintentional code-breaking must be reported, documented, and explained, and the name of the person who requested it must be provided to the Sponsor.

Although the ESDR performed when the 20 first subjects have received the first injection does not require the unblinding of data, unblinding can be performed at this review, if required. Moreover, some unblinded analyses may be provided by an independent Sanofi Pasteur statistician (ie, not involved either in the study or in the Dengue project) upon IDMC request.

A planned analysis will be performed on data collected up to 28 days post-Inj 3 of the last subject enrolled. This analysis will require the unblinding of data.

A second and final analysis will be performed at the end of the study.

Testing performed within GCI and GCI outsourced laboratories are blinded with respect to study treatment Group assignment. The code(s) linking information on sample vials to study treatment Group assignment are retained by the Clinical Department and cannot be accessed by GCI or contract laboratory testing personnel.

